8.2. Collection of variables

The main variable, degree of skin satisfaction/comfort, will be evaluated using the DLQI^{12, 13} questionnaire available in ANNEX II.

Mechanical sensitivity will be assessed by means of the Von Frey filament test in patients who voluntarily want to undergo it. The pain threshold and mechanical allodynia of patients with post-chemotherapy polyneuropathy will be measured before starting the study and once the chemotherapy treatment is over, expressing the threshold in the minimum number of pressure units that trigger pain in patients with the corresponding filament. of Von Frey approved.

The follow-up of the patients will be carried out through the usual oncological control during treatment. If the patients develop sensory or skin discomfort during this period, at the end of the treatment a check-up will be carried out using the following questionnaires:

- Follow-up of discomfort sensations available in a questionnaire derived from the Leonard Scale (ANNEX III).
- Degree of skin satisfaction by means of the Dermatology Life Quality Index [DLQI] (Annex II).
- Degree of satisfaction with the cream (Annex IV).

9. ADVERSE EVENTS

An adverse event is considered to be any adverse medical event that occurs in a clinical research subject to whom a product has been administered, even if it does not necessarily have a causal relationship with this treatment. An adverse event can also be any unfavorable or unexpected sign, including an abnormal laboratory finding, symptom, or illness temporarily associated with the use of an investigational product, related or not. An adverse event is considered to be any adverse medical event that occurs in a clinical research subject to whom a product has been administered, even if it does not necessarily have a causal relationship with its use. An adverse event can also be any unfavorable or unexpected sign, including an abnormal laboratory finding, symptom, or illness temporarily associated with the use of an investigational product, related or not.

Due to the fact the products in study are already commercialized, no adverse effects are expected. However, the recording of adverse events is an important aspect of study documentation, so the rules to follow are described below:

9.1. Detection and documentation of adverse events

Adverse events can be detected either by the subject himself or by the investigator, but it is the investigator's responsibility to record them. The Data Notebook will have a section for recording adverse events (Annex V) in which the investigator, or one of his collaborators, must describe events of this type in detail. The method of detecting adverse events can be either by direct communication from the subject under study, by exploration by the investigator, or by the subject's response to a question asked by the investigator or by any collaborator of the study.

In any case, the existence of an adverse event must be duly documented and the nature of the event, the date of detection and the start date if they do not coincide, the duration, severity and possible relationship with the event must be recorded at each visit. product under study.

The subjects in whom an adverse event is detected will be subjected to additional follow-up by the researchers, who will control the evolution of the adverse events until they have disappeared, decreased or stabilized. Follow-up information for these subjects should be brought to the attention of the study monitor.

In addition to documenting the occurrence of any unexpected events, investigators should assess their intensity based on the following scale:

- Mild: adverse event that causes minimal discomfort, tolerable by the subject and that does not interfere with their daily activities.
- Moderate: An adverse event bothersome enough to interfere with normal daily activities.
- Severe: event or adverse reaction that requires hospitalization of the subject or prolongs it, that endangers his or her life, causes invalidity or permanent incapacity, gives rise to some anomaly or congenital malformation, or that produces his or her death). For notification purposes, those suspected adverse events or adverse reactions that are considered important from a medical point of view, even if they do not meet the above criteria, will also be treated as serious.

Unexpected adverse reaction: adverse event whose nature or severity does not correspond to the information in the product's technical data sheet.

9.2. . Assessment of causality

The investigator should make every effort to explain each adverse event and assess its relationship, if any, to treatment with the study product. Causality should be assessed using the following categories:

- Definitive: The adverse event follows a reasonable time sequence from the time of product administration and follows a known response pattern of the study product and cannot be reasonably explained by other factors such as the subject's clinical condition or other therapeutic interventions or concomitant medications administered to the subject and, in addition, one or more of the following: a) appears immediately after administration of the drug; b) improvement when discontinuing drug administration; c) reappears upon reintroduction of the drug.
- Probable: The adverse event follows a reasonable time sequence from the time of product administration and follows a known response pattern to the study product and cannot be reasonably explained by other factors such as the subject's clinical condition or other therapeutic interventions or concomitant medications administered to the subject.
- Possible: The adverse event follows a reasonable time sequence from the time of administration of the product and/or follows a known response pattern of the product under study, although it could be caused by other factors such as the clinical condition

of the subject or other therapeutic interventions or concomitant medications administered to the subject.

- Unlikely: The adverse event is more likely to be caused by other factors such as the subject's clinical condition, therapeutic interventions, or concomitant medications administered to the subject and does not follow a known response pattern of the study product.
- Unrelated: The adverse event is clearly related to other factors such as the subject's clinical status, therapeutic interventions, or concomitant medications administered to the subject.

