9.3. Procedures for immediate notification of serious or unexpected events

A severe adverse event is considered to be any adverse medical event that at any dose:

- Causes the death of the subject.
- Puts life in danger.
- Requires hospitalization of the subject or the extension of an existing hospitalization.
- Causes significant or permanent disability/invalidity or a congenital abnormality/birth defect or overdose (accidental or deliberate). Produce la muerte del sujeto.

The principal investigator will immediately notify the promoter of all serious adverse events. The initial communication will be followed by detailed written communications. In the initial and follow-up communications, the study subjects will be identified by means of a specific code number for each of them. In the event that a death of a subject participating in a trial has been reported, the investigator will provide the promoter and the Clinical Research Ethics Committees involved with all the additional information requested.

The principal investigator will communicate serious and unexpected adverse events to the promoter by telephone, email or fax within 24 hours of the investigator becoming aware of the adverse event. The prior report made by telephone, email or fax must be followed by a complete report that includes a copy of the relevant data collected or recorded in the center or other documents produced as a result of the adverse event.

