ANNEX V: NOTIFICATION OF POSSIBLE ADVERSE REACTIONS

Subject identification:

Protocol	20PB-02	Nº notification	
Subject identification number		Report type	Initial  Follow-up 

Reaction Characteristics:

Study inclusion date:	Adverse Event Description:		
Date of first application:			
Date of adverse reaction appearance:			
Severity Adverse Reaction	Mild  Moderate  Severe 		
Consequence Adverse Reaction			

Information on the product under study:

Suspicious Product	Doe	Route	Starting date:
			End date:
Did the adverse effect subside when suspending the application of the product?			Did the effect reappear when applying the product again?
YES  NO  NOT APPLICABLE 			 YES  NO NOT APPLICABLE

Information to take into account and medical history:

Concomitant Medication	Reason of Prescription	Had the patient experienced or recorded the side effect before?	
		YES  NO 	
		When?	
		What was it related to?	
Other relevant data from the clinical history:			

Investigator Name:

Position:

Is additional documentation attached? YES NO

Which?

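### Section 9.1 defines its top intensity grade by seriousness outcomes, and sections 9.1, 9.3 and Annex V do not share one definition of a serious event

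*Combined protocol and SAP*

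**What the plan says.** Section 9.1 introduces a three-step scale with the instruction that "investigators should assess their intensity based on the following scale". The first two steps are "Mild: adverse event that causes minimal discomfort, tolerable by the subject and that does not interfere with their daily activities" and "Moderate: An adverse event bothersome enough to interfere with normal daily activities". The third opens "Severe: event or adverse reaction that requires hospitalization of the subject or prolongs it" and continues with danger to life, invalidity or permanent incapacity, congenital malformation and death. The same bullet adds a sentence beginning "For notification purposes, those suspected adverse events or adverse reactions that are considered important from a medical point of view", which brings such events in as serious even when no listed outcome is met.

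Section 9.3 has a heading that refers to serious *or* unexpected events. It opens its own list with "A severe adverse event is considered to be any adverse medical event that at any dose": death, danger to life, hospitalisation or its extension, significant or permanent disability, congenital abnormality, or overdose. It then requires immediate notification of all *serious* events, and a report within 24 hours of events that are serious *and* unexpected.

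Annex V, which section 9.1 names as the adverse event section of the Data Notebook, has a field labelled "Severity Adverse Reaction" with boxes for mild, moderate and severe. It also has open fields for the description and the consequence of the event.

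**The concern.** Intensity (how strong an event is) and seriousness (what it leads to) are separate properties. A scale meant for the first should not switch to the second at its top step. Here it does, so the recorded grade means one thing for Mild and Moderate and another for Severe.

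What is at stake is the safety record. By the compositions in sections 2.3 and 7.1, the two creams differ by one listed ingredient, present only in PB-011, so local skin tolerability is a natural safety comparison between the arms. If strong local reactions treated at home are recorded in the same category as merely bothersome ones, that comparison is blunted. In addition, section 9.1 defines an unexpected reaction partly by whether its severity matches the product information, so an outcome-based grade also muddies that judgement.

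The second problem is that the section carrying the notification duties does not use the same list of serious events, or the same word for it, as the section before it.

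**Working it through.** No arithmetic applies. The protocol gives no adverse event rates, and the point uses no sample size or power input. The check sets the texts side by side.

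**Step 1: what each grade in 9.1 measures.**

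| Grade | Criterion | Property measured |
|---|---|---|
| Mild | Minimal, tolerable discomfort; daily activities unaffected | Intensity |
| Moderate | Interferes with daily activities; no upper limit given | Intensity |
| Severe | Hospitalisation, danger to life, incapacity, malformation, death | Outcome |

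**Step 2: put two hypothetical events through the scale.**

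- A hand reaction stops a patient using the hands for several days, is managed at home, and leaves no lasting effect. It exceeds Mild and meets Moderate. It meets no Severe criterion. It is recorded as Moderate, like a reaction that is only bothersome.
- An event causing little discomfort prolongs a hospital stay. It meets the prolongation criterion and is recorded as Severe. It also fits the Mild description, and the scale gives no rule for choosing between the two; this assumes the highest grade met is the one recorded.

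**Step 3: compare the lists.**

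| Criterion | 9.1 | 9.3 |
|---|---|---|
| Death | Yes | Yes |
| Danger to life | Yes | Yes |
| Hospitalisation or its prolongation | Yes | Yes |
| Disability | Invalidity or permanent incapacity | Significant or permanent |
| Congenital abnormality | Yes | Yes |
| Medically important event | Yes, as serious, for notification | Not listed |
| Overdose | Not listed | Yes |
| Label on the list | Severe | Severe |
| Label in the notification duties | n/a | Serious |

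Two categories appear in one section only, and the disability wording differs. The term that triggers notification in 9.3 is not the term that 9.3 defines.

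**Step 4: follow a medically important event through to notification.** Section 9.1 says that such an event is to be treated as serious for notification. Section 9.3 requires immediate notification of all serious events. Read in sequence, the event is notified. The chain breaks only for someone who starts from the list in 9.3, or from the severity boxes in Annex V, without going back to 9.1.

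**Step 5: the 24-hour rule.** The heading of 9.3 joins serious and unexpected with *or*; the rule in its text joins them with *and*. Taken literally, these describe different sets of events.

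**Step 6: the form.** Annex V records one of three grades and free text. Nothing on it records whether the event was serious.

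**The case against.** The strongest reply concerns notification. A reader might infer that medically important events will not be reported at once. The documents do not support that: section 9.1 states that events "considered important from a medical point of view, even if they do not meet the above criteria, will also be treated as serious", the sentence containing those words opens by tying the rule to notification, and 9.3 applies to all serious events. What stands is narrower: 9.3 does not repeat the clause, so a centre relying on 9.3 or Annex V alone could overlook it.

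A reader might also infer that every reaction without hospitalisation is capped at Moderate. That is too broad, because danger to life or permanent incapacity also leads to Severe. The cap applies to intense reactions that meet none of the listed outcomes. Nor can one say that a planned severity table will be wrong: section 12 specifies no adverse event table or comparison.

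Two further replies have partial force. Annex V's open fields can hold a hospitalisation or a death, so seriousness may often be recoverable, but free text is not a classification. Annex IV asks patients to score discomfort and skin reaction from 1 to 10. However, sections 7.2 and 8.2 schedule it at the end of chemotherapy for patients who developed discomfort, so it does not replace the investigator's grading of each event.

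Finally, the mix of severe and serious may be a translation slip; untranslated Spanish remains inside the list in 9.3. That is plausible, but it does not rescue the scale. If the third bullet of 9.1 is read as Serious, the scale has no severe grade at all.

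**Conclusion.** The point holds in this form. The top grade in 9.1 does not measure intensity, so grading is distorted in both directions: downward for intense reactions with none of the listed outcomes, upward for low-intensity events that require or prolong hospitalisation. Sections 9.1 and 9.3 disagree on two categories (medically important events and overdose), on the disability wording and on the label, and the heading and text of 9.3 disagree on *or* versus *and*. Notification of medically important events is covered when the two sections are read together.

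The number of events affected cannot be derived from the documents. The effect is on safety grading and reporting; the sample size and the primary analysis are not affected. The statement about the form rests on Annex V as shown. The Data Notebook itself (Annex I) is a separate attachment, and if it has a seriousness field, the recording gap closes but the conflicting definitions remain.

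**What to change.** - **Section 9.1:** define Severe on the same ladder as Mild and Moderate, as a greater effect on daily activities than Moderate, and give Moderate an upper limit to match. Take the seriousness outcomes out of the intensity scale.
- **Sections 9.1 and 9.3:** use one list, headed serious, in both places. It should address medically important events and overdose explicitly and use one wording for disability.
- **Section 9.3:** reconcile the heading with the 24-hour rule, so that it is clear whether the rule applies to events that are serious and unexpected, or to either. The sponsor must decide which is meant.
- **Annex V:** add a serious yes/no box beside the severity field.

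The cost is wording in two sections and one checkbox, processed as an amendment under section 11.4. It needs no extra visits, staff or patients. If events have already been recorded, their grades should be rechecked against the description and consequence fields.

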9.3. Procedures for immediate notification of serious or unexpected events

A severe adverse event is considered to be any adverse medical event that at any dose:

- Causes the death of the subject.
- Puts life in danger.
- Requires hospitalization of the subject or the extension of an existing hospitalization.
- Causes significant or permanent disability/invalidity or a congenital abnormality/birth defect or overdose (accidental or deliberate). Produce la muerte del sujeto.

The principal investigator will immediately notify the promoter of all serious adverse events. The initial communication will be followed by detailed written communications. In the initial and follow-up communications, the study subjects will be identified by means of a specific code number for each of them. In the event that a death of a subject participating in a trial has been reported, the investigator will provide the promoter and the Clinical Research Ethics Committees involved with all the additional information requested.

The principal investigator will communicate serious and unexpected adverse events to the promoter by telephone, email or fax within 24 hours of the investigator becoming aware of the adverse event. The prior report made by telephone, email or fax must be followed by a complete report that includes a copy of the relevant data collected or recorded in the center or other documents produced as a result of the adverse event.

10. ETHICAL ASPECTS

10.1. General Considerations

This study must be carried out in accordance with the protocol and with the standards of good clinical practice, as described in:

- Harmonized Tripartite Standards of the ICH E6, for Good Clinical Practice of 1996.
- Regulation (EU) No 536/2014 of the European Parliament and of the Council, of April 16, 2014.
- ROYAL DECREE 1090/2015, of December 4, which regulates clinical trials with medicines, the Research Ethics Committees with medicines and the Spanish Registry of Clinical Studies.
- Declaration of Helsinki and amendments regarding medical research in human beings.

The researcher agrees, by signing this protocol, to follow the instructions and procedures described in it and therefore will comply with the principles of Good Clinical Practice on which it is based. Once the protocol is signed, it must not be modified without the written agreement of both the promoter and the principal investigator, and with the consent of the Research Ethics Committee.

A signed and dated document confirming that the protocol, the informed consent form and the patient information sheets have been approved by the Ethics Committee must be delivered to the promoter, together with the name and position of the president and members of the Ethics Committee.

10.2. Information to volunteers

The investigator must explain to each subject the nature of the study, its purposes, procedures, expected duration and the potential risks and benefits related to participation in the study, as well as any inconvenience that this may entail. Each of the participants must be informed that their participation in the study is voluntary and that they can withdraw from the study at any time, without this affecting their subsequent medical treatment or their relationship with their treating physician.

Informed consent will be provided in standard writing, in language easily understood by the participant. The subject must have sufficient time to read and understand the explanations before dating and signing the informed consent and must receive a copy of the signed

document. No subject can be included in the study without having previously given their informed consent.

10.4. Econocmic report

Given that there is no deviation from the conditions of use established in the product instructions, the center promoting the study (PROSPERA BIOTECH) will provide both creams to the subjects.

The detailed relation of the costs of this study is contemplated in ANNEX XI.

10.5. Insurance police

An insurance policy has been contracted with Berkley company with address at [name]. This insurance covers personal damage caused to the subjects as a result of the study, as well as economic damage arising directly from the same, in accordance with Royal Decree 1090/2015, of December 4. In addition to the legal civil liability of the study promoter, the legal civil liability of the researcher and his collaborators, that of the

hospital or center where the study is carried out, as well as that of the owner of the study, is covered.

11. PRACTICAL CONSIDERATIONS

11.1. Responsibilities of all study participants

Investigator: The investigators will abide by the Good Clinical Practice standards and will know and follow the Standard Operating Procedures (SOPs) of the relevant Clinical Trials Unit. All the information collected during the execution of the project will be recorded directly in the data collection notebook, which is attached as Annex I. When a correction is made, the date and the initials of the person who makes it must be noted.

Auxiliary Personnel: The auxiliary personnel will follow the instructions given by the investigator.

Monitor. The monitor must attest that the information compiled in the protocol is true, for which you must have all kinds of facilities from the research team to carry out their work.

Promoter: will be responsible for ensuring compliance with the relevant legal regulations and for supplying the product under study.

11.2. Protocol deviations

When a situation that causes a deviation from the protocol occurs, the deviation will be only for that subject. Investigators present in such circumstances will fully document the deviation and reason on the Data Notebook. In the event that the deviation has to do with the inclusion/exclusion criteria, the investigators will contact the clinical monitor by telephone in order to inform them of such deviation.

11.3. Collection and filing of documentation

There will be a documentation file for all the data, which will be kept for 5 years after the end of the study. This file must contain the following elements:

- Approval by the Ethical Committee of the protocol and the informed consent form.
- Copy of the written consent form and the approved protocol with any amendments if applicable.
- Any correspondence related to the study with the promoter, during the course of the study.

- Any correspondence with the Ethics Committee.
- Signed acceptance of the protocol.
- Curriculum vitae of the principal investigator and of the other investigators who make up the research team.
- Register of signatures of the members of the research team.
- Communications of serious adverse events.
- Contract between the promoter and the hospital when applicable
- Copies of Data Notebook.

